## SPECIFIC AIMS

Mild traumatic brain injury (mTBI) secondary to exposure to repetitive blast has been termed the “signature injury” of the wars in Iraq and Afghanistan. Recent autopsy case reports of the neuropathology of chronic traumatic encephalopathy (CTE) in five Iraq and Afghanistan Veterans with repetitive mTBI and demonstration of widespread tau pathology following a single blast exposure in a mouse model of blast mTBI increase the urgency of finding effective treatment to prevent neurodegeneration and dementia in Veterans with mTBI. In addition, head trauma is the clearest environmental risk factor for Alzheimer’s disease (AD), the common late-life neurodegenerative disorder. Finding a therapy to prevent CTE and reduce risk of AD in Veterans with TBI is a high priority.

Because the pathologic processes of CTE and AD start years to decades prior to clinical dementia, the challenge in prevention trials are: 1) developing tools to assess disease-modifying effects prior to clinical dementia; 2) recruiting and retaining a large cohort over a prolonged follow-up period (owing to the low incidence of CTE and AD in young age through early aging); and 3) assuring the safety of a potential disease-modifying drug being administered to large numbers of healthy subjects of which only a minority may be at risk of developing CTE or AD. For example, toxicity and side effects resulted in the cessation of a trial of naproxen and celecoxib for AD (the Alzheimer’s Disease Anti-inflammatory Prevention Trial).

The feasibility of primary prevention trials for neurodegenerative dementia may be improved by employing biological markers related to neurodegenerative processes in CTE and/or AD as surrogate outcomes. Cerebrospinal fluid (CSF) biomarkers are attractive surrogate end-points for prevention trials as they have proven sensitivity for the prediction of disease onset and, in addition, have the potential for providing information regarding the mechanisms of the preventive treatment. Using CSF biomarkers in a pilot study, we found that 14 weeks of simvastatin (a statin with high central nervous system [CNS] penetration) reduced CSF levels of total tau (t-tau), tau protein phosphorylated at threonine 181 (p-tau181) and amyloid  $\beta_{1-42}$  (A $\beta_{42}$ ), and showed a trend for increasing brain-derived neurotrophic factor (BDNF, a growth factor which promotes neuronal survival, growth and synaptic plasticity) in cognitively normal hypercholesterolemic middle-aged subjects compared to the treatment with pravastatin (a statin with low CNS penetration). **This pilot study suggests that the innovative use of CSF biomarkers as surrogate outcomes in a prevention trial is feasible.**

Statins are attractive therapeutic agents for neurodegenerative dementia primary prevention trials because: 1) they have demonstrated safety and tolerability in healthy subjects at risk for cardiovascular disease, including those with normal cholesterol levels; 2) epidemiologic studies from our laboratory and others indicate that statin use is associated with reduced risk of clinical dementia and AD as well as reduced neurofibrillary tangle (NFT) burden at autopsy; 3) neuroprotective effects of statins have been shown in TBI animal models and in observational studies of functional recovery in older TBI victims; and 4) our pilot study of simvastatin demonstrated reduction in CSF biomarkers related to tau pathology that could be detected after as little as 14 weeks of treatment.

We propose a 12-month, double-blind, randomized, placebo-controlled trial to establish *proof-of-concept* for use of simvastatin (40 mg/d) for decreasing CSF biomarkers of neurodegeneration and increasing CSF neurotrophins in 120 Iraq and Afghanistan Veterans with repetitive blast mTBI. Specific Aims are:

**Specific Aim 1: To examine the effects of 12 months of treatment with simvastatin 40 mg/day on CSF concentrations of tau biomarkers (t-tau, p-tau181, and t-tau:p-tau181 ratio) and BDNF in Iraq and Afghanistan Veterans with repetitive blast concussion mTBI.**

Hypothesis 1: Compared to placebo, simvastatin will reduce levels of CSF t-tau, p-tau181, and p-tau181:t-tau ratio; and will increase level of CSF BDNF.

**Specific Aim 2: To explore the effects of 12 months of treatment with simvastatin 40mg/day on CSF A $\beta_{42}$ , and biomarkers of oxidative stress and neuroinflammation in Iraq and Afghanistan Veterans with repetitive blast concussion mTBI.**

Hypothesis 2: Compared to placebo, simvastatin will reduce levels of CSF A $\beta_{42}$ , and biomarkers of oxidative stress (F2-isoprostanes) and neuroinflammation (interleukin [IF]-6, IL-8, and S100 $\beta$ ).

Because of concerns regarding potential adverse effects of statins, we will administer a neurocognitive test battery to monitor memory and other cognitive functions during the study period. We will also monitor potential effects of simvastatin treatment on persistent postconcussive symptoms (PPCS), posttraumatic stress disorder (PTSD), depression, alcohol use, functional status, and health-related quality of life. **The findings of the proposed study may provide, in a relatively short period of time, proof-of-concept in support of larger scale primary prevention trials to prevent neurodegeneration and dementia in Iraq and Afghanistan Veterans and service members with repetitive mTBI.**

## RESEARCH DESIGN AND METHODS

**Overview:** The proposed study is a 12-month, double blind, randomized placebo-controlled trial of simvastatin (40 mg/day) vs. placebo in Iraq and Afghanistan Veterans with repetitive blast mTBI with PPCS). We will use National Institute of Neurological Disorders and Stroke Common Data Elements (NINCDS CDE) Core and selected Supplemental measures relevant to mTBI from the as well as additional assessments. The study definition of mTBI will follow ACRM criteria, defined as a traumatically induced physiologic disruption of brain function manifested by at least one of the following: loss or alteration of consciousness lasting less than 30 minutes; any loss of memory for events immediately before or after the accident with any posttraumatic amnesia lasting not more than 24 hours; initial Glasgow Coma Scale score  $\geq 13$ . Although most participants will have multiple exposures, they will be considered to have mTBI if any single exposure meets these criteria. Because Glasgow Coma Scale scores in the combat setting will be unavailable, this criterion will not be required if other criteria for mTBI are met.

Primary outcomes are change in concentration of CSF t-tau, p-tau181, p-tau181:t-tau ratio, and BDNF. The secondary outcomes include change in concentration of CSF biomarkers of amyloid deposition: A $\beta$ 42; oxidative stress: F2-isoprostanes; and inflammation: IL-6, IL-8, and S100 $\beta$ . Potential cognitive adverse effects of statin treatment will be assessed by psychometric measures of simple and sustained attention, working and declarative memory, and complex reasoning. Primary and secondary CSF biomarker outcomes and neuropsychological tests will be measured at baseline and 12-months of treatment. Customary clinical monitoring for clinical response and for adverse effects (including CPK and hemoglobin A1C) will be monitored at 6-weeks and at 3-, 6-, 9-, and 12-months of treatment. Compliance will be monitored with pill counts at each visit.

**Participants:** 120 Iraq and Afghanistan Veterans who meet study inclusion/exclusion criteria will be enrolled. Persons of all races and ethnicities and both genders will be eligible. Participants will be naïve for statins, and will have either normal LDL cholesterol or mildly elevated LDL cholesterol which does not require drug therapy per National Cholesterol Education Program Adult Treatment Panel III (NCEP/ATP-III) guidelines.

### *Inclusion Criteria for all participants:*

- Males and females ages 21-50 years.
- Documented hazardous duty in Iraq and or Afghanistan with the U.S. Armed Forces.
- Exposure to one or more blast trauma events resulting in mTBI according to ACRM criteria as defined above.
- More than 6 months since last blast trauma exposure
- Ability to complete psychometric and other clinical assessments in English (i.e., adequate English language skills, vision and hearing).
- Normal or mildly elevated cholesterol which does not require drug therapy based on NCEP/ATP-III guidelines (i.e., fasting LDL <190 for those with  $\leq 1$  cardiovascular risk factor and < 160 for those with 2+ risk factors).
- No use of statins during the previous year and no recent (past 4 weeks) use of other lipid-lowering drugs (e.g., fibrates, niacin > 500mg/d, or high dose omega-3 fatty acids) preceding randomization.
- No clinically significant laboratory abnormalities (electrolytes, glucose, carbon dioxide, BUN, creatinine, vitamin B12, folate, albumin, thyroid stimulating hormone).
- Platelet count > 100,000/mm^2.
- Body Mass Index (BMI) between 18 and 36 inclusive (BMI outside this range would affect biomarker measurements or make LP difficult to perform).

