### *Exclusion criteria for all Participants:*

- History of head trauma with LOC > 30 minutes, or with a penetrating head wound, or with moderate to severe memory or other cognitive impairment.
- Neurological disorders: multiple sclerosis, epilepsy, stroke, PD, other degenerative CNS disorders, or neuropathy with radicular involvement.
- Acute or chronic major psychiatric disorders: schizophrenia, bipolar disorder or severe major depressive disorder, or severe anxiety disorder except PTSD and panic disorder (PTSD and depressive symptoms are common co-morbid conditions for combat mTBI and a subset of these patients have symptoms consistent with panic disorder as well).
- Use of illegal drugs; alcohol abuse within the past 6 months.
- Poorly controlled hypertension, heart failure, coronary heart disease, peripheral artery disease, carotid artery disease, diabetes mellitus, pulmonary disease with hypoxia or hypercapnia,

significant hepatic disease or hepatitis C seropositivity, renal failure, treatment for cancer, HIV positive, active infectious disease or presence of abdominal aortic aneurysm.

- Contraindications to LP (e.g., spinal cord injury; deformity, severe disease or infection in the region of the lumbosacral spine; bleeding tendency, use of anticoagulant medications, or platelet count <100,000/mm^2).
- Receiving medication in an investigational drug study.
- Exclusionary medications (used in the 4 weeks prior to screening):
  - Fibrates and niacin due to increased risk for myopathy in combination with statins;
  - Potential drug-drug interactions with statins via effects on CYP3A4: itraconazole, ketoconazole, erythromycin, clarithromycin, HIV protease inhibitors, nefazodone, amiodarone, cyclosporine, isoniazid, quinidine, or large quantities of grapefruit juice (>1 quart daily);
  - Selected CNS-acting medications: antipsychotics, anti-Parkinson's disease medications and CNS stimulants
  - Other medications affecting coagulation and/or inflammation: coumadin, potent anti-inflammatory medications (hydrocortisone, methotrexate or other potent immune-modulating medications), and anti-HIV medications.
- All female subjects of childbearing potential will undergo a urine pregnancy test at every subject visit; subjects with positive pregnancy test results will be excluded. In addition, all female subjects of childbearing potential will be required to use a reliable method of contraception throughout the duration of the study.

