Description of Recruitment Process: Participants will be recruited from the MIRECC Mild TBI/Behavioral Specialty Clinic; Deployment Health Clinic, Polytrauma Clinic, General Internal Medicine Clinic, and Mental Health Clinics at VA Puget Sound; the Seattle downtown Vet Center; community-based outpatient clinics (CBOCs), and from outreach to National Guard and Reserve units. Recruitment will be assisted by posters, flyers, brochures, announcements in the VA daily bulletin, and print and radio media advertising. Prospective participants will have their charts reviewed by referring providers to screen for exclusionary medical conditions and medications.

Potentially eligible persons will be referred to the study team for obtaining informed consent. Written informed consent will be obtained from participants by the PI, study Co-Investigator, or Study Coordinator. If a potential participant's primary mental health care provider is a study investigator, another investigator will conduct the consent process. Care will be taken to assure participants that research study participation is voluntary and their current treatment and future services and benefits are not contingent on participation in this or any research study.

Participants will receive compensation for their time and inconvenience as follows: \$50 for the screening visit, \$50 for each cognitive testing day, \$200 for each LP day, and \$25 for each safety visit. The total each subject will receive if all study visits are completed is \$650. Subjects who withdraw early or are withdrawn from the study will receive pro-rated payments based on the number of study visits completed.

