## PROTECTION OF HUMAN SUBJECTS

### (1) Risk to Subjects

(a) Human Subjects Involvement and Characteristics: Participants will be 120 Iraq and Afghanistan Veterans between the ages of 21 and 50 who are in good general health and who meet the specific study inclusion/exclusion criteria as described in detail in the "Research Design and Methods" section above. Persons of all races and ethnicities and both genders will be eligible. Participants will be naïve for statins, and will have either normal LDL cholesterol or mildly elevated LDL cholesterol which does not require drug therapy per NCEP/ATP-III guidelines.

Specific inclusion criteria include documented hazardous duty in Iraq and/or Afghanistan with the U.S. Armed Forces and exposure to blast concussion (with >6 months since last blast exposure) sufficient to meet ACRM criteria for mTBI (*described in detail above*). Participants will have a BMI between 18 and 36 (BMI outside this range may affect the biomarker measurements and increase difficulty of LP).

Exclusion criteria for all participants will include: penetrating head wound; seizure disorder; insulin-dependent diabetes; alcohol abuse or other substance abuse; DSM-IV diagnosis of schizophrenia or other psychotic disorder, bipolar disorder, or dementia; use of exclusionary medications (used in the 4 weeks prior to screening) or receiving any investigational medication; contraindication to LP (spinal deformity, severe lumbar spine disease or infection at LP site, bleeding tendency or on anticoagulant medication); platelet count less than 100,000 at time of LP.

Women of childbearing potential must have a negative pregnancy test at screen and must agree to use an acceptable form of birth control for the duration of the study. We suggest that women continue to use birth control for one full menstrual cycle after completing or withdrawing from the study.

It is likely that economically disadvantaged subjects will participate in this study. This may be considered a vulnerable population. While subjects will receive up to \$650 for completion of the study, it is not felt that degree of remuneration will represent any form of economic coercion to those that are economically disadvantaged, considering the potentially significant time commitment we are asking the subjects to make. Prisoners and institutionalized individuals will not be involved in this study.

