(b) Sources of Materials: Research materials from living human subjects will be results from clinical/neuropsychiatric assessments; blood samples collected for screening labs, DNA, and biomarker analysis; and CSF collected for biomarker analysis. These procedures will be done specifically for research purposes. In addition, existing medical records will be reviewed to confirm eligibility for participation. Consent will be obtained before reviewing existing medical records.

(c) Potential Risks: Risk to subjects is modest. All risks are research risks, none are therapeutic risks. They include possible stress from undergoing clinical/neuropsychiatric assessment, risks of blood draw/i.v. placement, LP, risks of taking simvastatin, and potential loss of confidentiality.

*Risks of Simvastatin*: Simvastatin is used widely for lowering cholesterol and for primary prevention of cardiovascular and cerebrovascular disease at the doses proposed in this application. It is generally safe and well tolerated. The most common adverse effects in clinical use are elevated liver transaminases, myalgias, and elevated CPK. However, the literature suggests that the rate of adverse reactions necessitating withdrawal from statin therapy is less than one percent in clinical practice. Simvastatin is classified by the US FDA as Pregnancy Category X and is contraindicated in women who are pregnant or nursing. All female subjects of child bearing potential will have urine pregnancy tests at every study visit, will be required to be using a reliable form of contraception, and will be told of the risks of becoming pregnant while participating in this study. We also advise women of childbearing potential that they wait one full menstrual cycle after stopping the medications offered in this study before becoming pregnant.

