**(b) Protection Against Risk:**

*Reduction of risks related to simvastatin:* All study participants will have either normal or mildly elevated cholesterol not meeting current NCEP guidelines for treatment with cholesterol lowering medications. Simvastatin has been widely used for primary or secondary prevention of cardiovascular diseases. Although we will treat subjects with non-elevated cholesterol, adverse effects related to excessively low cholesterol levels are not anticipated, as recent trials with high doses of potent statins producing very low levels of LDL-cholesterol have shown that such low LDL-cholesterol serum levels are generally safe and, in fact, are associated with improved clinical outcomes in terms of coronary artery disease.

Simvastatin is classified by the US FDA as Pregnancy Category X and is contraindicated in women who are pregnant or nursing. All female subjects of child bearing potential will have urine pregnancy tests at every study visit and will be told of the risks of becoming pregnant while participating in this study. We consulted with pharmacist at VA Puget Sound whether a woman should wait for a certain period after ceasing statin drug before becoming pregnant and he suggested 16 days (the elimination half-life of radioactive simvastatin plus metabolites in humans is 4.5 hours. Assuming 95% of the drug and metabolites are eliminated after 5 half-lives, then 16 days could be considered safe). We are erring on the safe side and suggesting that women of childbearing potential wait one full menstrual cycle after stopping the medications offered in this study before becoming pregnant. Contraception is not required for male participants.

At randomization, subjects will be advised of potential drug-related side effects from simvastatin such as muscle pain and weakness and nausea or vomiting. They will be counseled on the importance of letting the study personnel know which medications they are currently taking and that they should inform the study staff before initiating any new medication treatment. Subjects will be told that many medications should not be taken with simvastatin and that they should not drink large quantities of grapefruit juice while in the study (as intake of large quantities of grapefruit juice may result in elevated simvastatin serum levels). Subjectst will also be advised to avoid drinking excessive amounts of alcohol.

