*Safety procedures specific to the war zone population:* include exclusion of participants with severe psychiatric instability or severe situational life crises, including evidence of being actively suicidal or homicidal, or any behavior that poses an immediate danger to patient or others. For participants enrolled in the study, requiring psychiatric interventions to manage deterioration of clinical status will result in early study termination, and appropriate crisis management by a study clinician, in conjunction with the participant's primary mental health care provider and referral to outpatient or inpatient psychiatric care at each study site. The PI (or back-up) will be on call at all times to receive calls from participants regarding any adverse events; participants will be provided with 24-hour emergency phone numbers.

In addition, due to the increased scrutiny surrounding studies of persons with comorbid depression, we will specifically ask about suicidal ideation at each study visit. Subjects who endorse suicidal ideation will be assessed as to their level of risk and the level of care required to keep themselves or others from harm. If a patient requires inpatient treatment in order to prevent harm but is unwilling to accept that care, referral will be made to the county-designated Mental Health Professional (MHP) and the patient will be supervised in a safe setting in the VA Puget Sound emergency room until evaluated by the MHP and appropriate disposition made. In a similar fashion, patients that are found to have symptoms of disorganized thought processes secondary to psychosis would be referred for an emergency psychiatric evaluation at VA Puget Sound.

*Treatment of Adverse events:* All treatment for adverse events related to the study will be provided free of charge. DVA authorizes treatment for any study approved by a VA R&D Committee. Subjects who seek treatment for study-related adverse events in a non-VA facility will be reimbursed for treatment costs. VA Puget Sound has adequate personnel and equipment to respond to expected and unexpected adverse events.

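### The protocol calls simvastatin contraindicated in nursing women but does not exclude them; as a lesser point, CPK and transaminases are drawn at screening but not named in the laboratory entry criterion

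*Combined protocol and SAP*

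**What the plan says.** **Nursing.** Under Potential Risks (Risks of Simvastatin), and again under Protection Against Risk, the protocol states that simvastatin "is contraindicated in women who are pregnant or nursing". The measure that follows in the second place is: "All female subjects of child bearing potential will have urine pregnancy tests at every study visit and will be told of the risks". The risks meant there are those of conceiving while on study. The exclusion criteria say that "subjects with positive pregnancy test results will be excluded" and require reliable contraception. The shorter eligibility summary under Risk to Subjects says: "Women of childbearing potential must have a negative pregnancy test at screen and must agree to use an acceptable form of birth control". The criteria for termination from study include a positive pregnancy test. None of these mentions nursing.

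**CPK and transaminases.** The Screening visit text and Table 3 have CPK and liver tests drawn at screening. The criteria for termination remove a subject who develops SGOT or SGPT above 3 times, or CPK above 10 times, the upper limit of normal (ULN). Protection Against Risk stops study drug at or above the same multiples. The laboratory inclusion criterion begins "No clinically significant laboratory abnormalities (electrolytes, glucose, carbon dioxide, BUN, creatinine" and ends with vitamin B12, folate, albumin and TSH. The exclusion criteria separately bar serious liver disease and positive hepatitis C serology.

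**The concern.** A contraindication is normally carried into the exclusion list, so that whoever screens a candidate has a rule to apply. Here the pregnancy half of the sentence became rules and the nursing half did not. All participants are volunteers and the protocol treats every risk as a research risk, so keeping the drug from a woman for whom the protocol calls it contraindicated should not depend on someone remembering a sentence in the risk narrative.

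For CPK and SGOT/SGPT, a screening result is obtained but no specific criterion says what an abnormal value means for entry. A subject could in principle start study medication with a value at which the protocol would stop it.

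**Working it through.** This is a check of the text, and the plan has no figure to reproduce. Setting entry rules beside on-study rules:

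| Item | Entry rule | On-study rule |
|---|---|---|
| Pregnancy | Positive test excludes; contraception required | Test at every visit; positive test removes |
| Nursing | None | None |
| CPK | Drawn at screening; not in the laboratory list | Stop level 10 × ULN |
| SGOT/SGPT | Drawn at screening; not in the laboratory list; liver disease and hepatitis C exclusions give partial cover | Stop level 3 × ULN |

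**Nursing, step by step.**
1. Women aged 21 to 50 are eligible.
2. A urine pregnancy test does not detect nursing, and using contraception does not rule it out.
3. Exclusions also appear outside the main lists, under the safety procedures for the war zone population, but they are psychiatric: "exclusion of participants with severe psychiatric instability or severe situational life crises".
4. Before referral, candidates have their "charts reviewed by referring providers to screen for exclusionary medical conditions and medications". Nursing is not a listed exclusion, so this review has no instruction to look for it.
5. Table 3 has no nursing question at any visit. The medical history may bring it up, but no rule then says what to do.
6. A woman who gave birth during the study should already have been removed by a positive pregnancy test. The case that matters is therefore a woman already nursing at screening, and one question there closes nearly all of the gap.

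**CPK and SGOT/SGPT, step by step.**
1. The laboratory criterion names nine items: electrolytes, glucose, carbon dioxide, BUN, creatinine, vitamin B12, folate, albumin and TSH. The list carries no *for example*, so it reads as complete.
2. After screening, Table 3 next schedules CPK and liver tests at 6 weeks of treatment.
3. Doses before that test: 6 × 7 = 42 nightly doses. Titration takes about 2 × 7 = 14, leaving 42 − 14 = 28 at the 40 mg level. These are simvastatin only in the active arm, about half of subjects (50 of 100 expected completers).
4. Interval from the screening test to the next one: at least about 6 weeks. The Baseline visit falls within 4 weeks of screening, and its two appointments within a week of each other. If both appointments fall inside the 4 weeks, the maximum is 4 + 6 = 10 weeks. If only the first must, it is 4 + 1 + 6 = 11 weeks. The text does not settle which.

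**Frequency.** The section on inclusion of women says that fewer than 25% of Military Police participants would be women and that the other three main specialties are all male. This shows that few women are expected. It gives no number of nursing women, and none can be derived. No screening distribution of CPK or SGOT/SGPT is given either.

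**The case against.** The strongest case on the other side has four parts.

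- **The contraindication is in plain sight.** It appears twice, once under risk reduction, so any clinician applying the protocol is told. The consent pages were removed from the public document and may cover nursing. This stands as mitigation, but a risk narrative or a consent warning is not an eligibility rule.
- **The CPK stop level is not an entry limit.** A reader might infer that the protocol set a baseline CPK limit and failed to carry it into the criteria. The documents do not support that. The 10 × ULN figure applies to subjects who develop an elevation on study, so no entry limit was dropped. What remains is that a test drawn at screening has no stated role in eligibility.
- **Judgement would intervene.** Participants must be people "who are in good general health and who meet the specific study inclusion/exclusion criteria", which adds a general-health condition to the specific criteria. An investigator reviews laboratory results within 24 hours, there is a brief physical examination at baseline, and symptoms prompt extra visits. A reader might infer that subjects beyond the stop level will be dosed. These safeguards make that unlikely. They do not replace a rule, because the written action on a high value is to discontinue study drug, which does not govern entry.
- **Tighter numeric limits lack support.** A reader might want, say, half the stop level as the entry limit. The documents give no basis for any such value, and the choice belongs to the sponsor.

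**Conclusion.** The nursing omission is clear from the text: a contraindication stated twice has no matching exclusion, screening question or termination rule. The CPK and SGOT/SGPT point is secondary, and weaker for the transaminases because the liver exclusions partly cover them. It rests on reading the bracketed laboratory list as complete, which is the literal reading. Both together are a low-severity participant-safety correction. The number affected is probably very small and may be zero. Nothing here bears on the primary biomarker comparison, the sample size or the efficacy conclusion, and nothing in the documents shows that an ineligible subject would in practice be treated.

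**What to change.** 1. Add nursing or breastfeeding to the exclusion criteria and to the eligibility summary under Risk to Subjects, and ask about it at screening.
2. Add CPK, SGOT and SGPT to the laboratory inclusion criterion, so that a clinically significant screening elevation bars randomisation. State that, at minimum, any value at or above the stop level (10 × ULN for CPK, 3 × ULN for SGOT or SGPT) does so. Saying at or above covers both forms of the stop rule, which is a strict inequality in the termination criteria and an inclusive one under Protection Against Risk. Any tighter limit is for the sponsor to set.

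The cost is wording, one question, and use of results already obtained. The downside is an occasional screen failure. No new visit or scheduled test is needed.
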